## **5. RANDOMIZATION AND BLINDING**

### **5.1 Randomization**

Eligible participants were randomized to the intervention or control group using a computer-generated random selection method. Randomization was performed individually for each participant immediately after completion of pre-test measurements and prior to the onset of foot care. This approach minimized selection bias.

### **5.2 Blinding**

A single-blind design was adopted. Outcome measurements (vital signs, state anxiety, pain) were performed by an independent assessor who was blinded to group allocation. Participants and the primary investigator administering the VR intervention were not blinded due to the nature of the intervention.

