### **3. STUDY DESIGN**

This study is a single-center, randomized controlled experimental trial with a pre-test/post-test design, conducted at Malatya Turgut Ozal University Training and Research Hospital (Orthopedics Unit and Chronic Wound Care Unit), Malatya, Turkey.

Study Period: December 9, 2024 - June 15, 2025

Study Design: Randomized Controlled Trial (RCT)

Blinding: Single-blind (outcome assessor blind to group allocation)

Allocation: Random (computer-generated block randomization list)

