### **7.4 Data Collection Procedure**

Data were collected at two time points using a face-to-face interview technique by the principal investigator:

Pre-test: Approximately 5 minutes before the start of foot care (after a minimum 5-minute rest period in the seated position). The Vital Signs Form, STAI-I, and VAS were administered. Participants were then randomized.

Post-test: Immediately after completion of foot care (within 0-2 minutes). The Vital Signs Form, STAI-I, and VAS were re-administered.

To ensure measurement standardization, all measurements were performed by the same researcher using the same equipment with participants in the same position. For blood pressure measurements, patients had rested for  $\geq 5$  minutes in a seated position and had abstained from caffeine for  $\geq 1$  hour and smoking for  $\geq 15$  minutes prior to measurement.

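### Sections 3 and 5.2 claim a blinded independent outcome assessor, but Section 7.4 has the principal investigator collecting the data, so the single-blind claim is unsupported until the sections are reconciled

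*Combined protocol and SAP*

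**What the plan says.** Three sections of the combined protocol and SAP bear on who measured the outcomes.

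- **Section 3 (Study Design)** gives the design label: "Blinding: Single-blind (outcome assessor blind to group allocation".
- **Section 5.2 (Blinding)** repeats it in operational terms: "Outcome measurements (vital signs, state anxiety, pain) were performed by an independent assessor who was blinded to group allocation". It then says who was not blinded: "Participants and the primary investigator administering the VR intervention were not blinded due to the nature of the intervention".
- **Section 7.4 (Data Collection Procedure)** describes the fieldwork: "Data were collected at two time points using a face-to-face interview technique by the principal investigator". On standardization it adds: "all measurements were performed by the same researcher using the same equipment with participants in the same position". At the post-test, "The Vital Signs Form, STAI-I, and VAS were re-administered", within two minutes of the end of foot care.

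Sections 7.1 and 7.2 list the outcomes. Pain (VAS) and state anxiety (STAI-I) are primary. Temperature, SpO2, pulse, respiratory rate and blood pressure are secondary. Respiratory rate is counted by an observer; the others in the secondary list are read from devices.

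**The concern.** Assessor blinding is the only blinding this trial claims, and the claim appears twice. The section that describes how the data were gathered names a different measurer and mentions no separate assessor. That section covers every primary and secondary outcome.

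If Section 7.4 describes what happened and the measurer knew the allocation, outcomes that depend on how the observer asks or counts could drift in favour of VR. The most exposed are VAS and STAI-I, collected face to face, and respiratory rate. A report that repeated the single-blind label would then claim a protection the trial did not have.

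**Working it through.** The plan gives no figure to reproduce on this point, so the main check is a comparison of the text.

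**Step 1: who measured, and what they knew.**

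| Question | Sections 3 and 5.2 | Section 7.4 |
|---|---|---|
| Who took the outcomes? | An independent assessor | The principal investigator |
| Did that person know the allocation? | No | Not stated |
| Which outcomes? | Vital signs, anxiety, pain | Vital Signs Form, STAI-I, VAS |
| How many measurers? | One assessor is described | One researcher for everything |
| Who gave the VR? | The primary investigator, unblinded | Not stated |

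**Step 2: can both columns be true?** Section 5.2 writes *primary* investigator and Section 7.4 writes *principal* investigator. The documents do not say whether these are the same person.

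- If they are one person, the person who gave the VR also collected the post-test data and was unblinded. Section 5.2 is then false as written, or Section 7.4 is.
- If they are two people, the measurer is still the trial's principal investigator, whom it is hard to describe as independent. Nothing says how that person was kept from learning the allocation, although the headset was worn throughout foot care (Section 6.1) and the post-test followed within two minutes.

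The contradiction rests on the sentence naming the principal investigator. The same-researcher sentence alone would fit a single independent assessor. It matters because, read with the other sentence, it leaves no room for a second measurer.

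**Step 3: which data are exposed?** Sections 5.1 and 7.4 both place randomization after the pre-test, so pre-test values cannot reflect knowledge of the allocation. Post-test values can. Section 8.4 compares post-test minus pre-test between groups, so any post-test bias passes straight into that comparison. The baseline comparison in Section 8.2 would not reveal it.

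**Step 4: how much could it matter? Illustration only.** Assume no true effect and a between-group bias of δ standard deviations of the change score, the quantity tested in Section 8.4. With n = 32 per group (Section 4.4), a two-sided 5% t-test has 2 × 32 − 2 = 62 degrees of freedom and a critical value of 1.999. The noncentrality is δ × √(n/2) = δ × √16 = 4δ.

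| Assumed δ | Noncentrality 4δ | Chance of a significant result | δ as a share of the planned d = 0.46 |
|---|---|---|---|
| 0 | 0 | 5.0% | 0% |
| 0.1 | 0.4 | 6.8% | 0.1/0.46 = 22% |
| 0.2 | 0.8 | 12.4% | 0.2/0.46 = 43% |
| 0.3 | 1.2 | 21.9% | 0.3/0.46 = 65% |

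The values of δ are assumptions with no source in the documents. They also do not separate assessor bias from participants' own expectations, which would remain even with a blinded assessor. The table shows that a modest bias would matter at this sample size. It does not measure the cost of this contradiction.

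**The case against.** The strongest reply is that the documents never say the person collecting data in Section 7.4 was unblinded. A reader might infer that the unblinded VR-giver took all the measurements and that the single-blind claim is therefore false. The documents do not go that far. They contain two incompatible accounts without showing which was carried out, and they do not equate the primary with the principal investigator. This stands, and it limits the conclusion to unsupported.

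A reader might also infer that every outcome was obtained by interview. Section 7.2 rules that out: vital signs were taken by device or by counting. Nor does face-to-face collection show that STAI-I, a self-report scale, was wrongly administered. A form can be handed over and completed in the assessor's presence. The mode of completion is unclear, not contradictory.

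Finally, it can be said that self-rating by participants who know their group is unavoidable when a headset is compared with none, that Section 5.2 openly says participants were unblinded, and that Section 3 confines the blinding claim to the assessor. That is fair. It makes self-rating a disclosed limitation deserving one line in the report, not a flaw in the plan.

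None of these replies removes the core conflict. No other section reconciles 5.2 with 7.4.

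**Conclusion.** The point holds as an internal contradiction about a stated design property. Until Sections 3, 5.2 and 7.4 are reconciled, the claim of a blinded independent assessor is unsupported for all outcomes at the post-test, and so for every change-score comparison in Section 8.4.

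That the two sections cannot both be true assumes that primary and principal investigator mean one person. If they do not, the weaker conclusion remains: the named measurer is not evidently independent, and no safeguard for that person's blinding is described. The amount of bias, if any, cannot be determined from the documents.

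This must be corrected before results are reported as single-blind, because the answer changes what may be concluded and the correction is cheap.

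**What to change.** Establish from study records who took the post-test measurements and whether that person knew the allocation. Then make Sections 3, 5.2 and 7.4 say the same thing, using one term for each role.

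- **If the measurer gave the VR or otherwise knew the allocation:** replace single-blind with open-label. Qualify the conclusions on VAS, STAI-I and the counted respiratory rate as unblinded assessments. Present the device-read vital signs (temperature, SpO2, pulse, blood pressure) as less observer-dependent.
- **If a blinded independent assessor was used:** correct Section 7.4 to name that role, and say how the assessor was kept unaware of allocation.
- **In either case:** state in one line that VAS and STAI-I are self-ratings by unblinded participants, which assessor blinding does not fully protect.

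Changing how the scales are completed is no longer a practical remedy, since Section 3 gives a study period ending June 15, 2025 and Section 4.4 reports 64 completers already analysed.

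The cost is one fact to establish, wording in three sections and, under the first outcome, a weaker blinding claim. No new participants or analyses are needed.

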## **6. INTERVENTIONS**

### **6.1 Intervention Group - Virtual Reality Application**

Participants in the intervention group wore a VR headset (VR Shinecon G40E 3D VR goggles paired with a Samsung Galaxy A30 smartphone) throughout the duration of the diabetic foot care procedure. A curated library of relaxing, nature-themed 360 degree virtual environments was available for patients to choose from. VR content had been selected and piloted prior to the study for acceptability, absence of motion sickness, and suitability for the clinical setting.

Infection control measures: The VR headset was cleaned and disinfected before and after each use according to hospital infection control protocols. Contact surfaces were wiped with single-use 70% isopropyl alcohol disinfectant wipes and allowed to dry completely. Single-use earpad covers were applied for each participant and disposed of as medical waste after use.

### **6.2 Control Group - Standard Care**

Participants in the control group received routine standard diabetic foot care without any additional intervention. No VR or other distraction technique was applied.

## **7. OUTCOME MEASURES AND DATA COLLECTION INSTRUMENTS**

### **7.1 Primary Outcomes**

Pain level: Visual Analog Scale (VAS) - a 10 cm horizontal line anchored at 0 ('no pain') and 10 ('worst imaginable pain'), developed by Price et al. (1983). Scores recorded to 0.1 cm precision.

State anxiety: State-Trait Anxiety Inventory - State subscale (STAI-I), a validated 20-item self-report scale scored 20-80, with higher scores indicating greater anxiety (Spielberger et al., 1970).

### **7.2 Secondary Outcomes (Vital Signs)**

- Body temperature (degrees C) - non-contact infrared thermometer (Life Net Medical JA-11C)
- Oxygen saturation / SpO2 (%) - fingertip pulse oximeter (Life Net Medical PFX033)
- Pulse rate (beats/min) - pulse oximeter
- Respiratory rate (breaths/min) - direct observation and counting

- Systolic blood pressure (mmHg) - upper-arm automated sphygmomanometer (Omron M3 Comfort HEM-7155-E)
- Diastolic blood pressure (mmHg) - same device

### **7.3 Demographic Data**

A Demographic Information Form was used to collect participant characteristics including age, sex, education level, duration of diabetes, wound grade, and analgesic medication use.

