### **8.2 Between-Group Comparisons at Baseline**

Independent samples t-test was used for continuous variables and chi-square test for categorical variables to verify baseline comparability of the intervention and control groups.

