### **8.4 Between-Group Comparisons of Change Scores**

Independent samples t-test was used to compare the magnitude of change (post-test minus pre-test) between the intervention and control groups for each outcome variable.

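### Wound grade and baseline analgesic use are collected but left out of the between-group comparison, which costs precision and leaves any chance imbalance uncorrected

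*Combined protocol and SAP*

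**What the plan says.** - Section 7.3: the Demographic Information Form records, among other items, "duration of diabetes, wound grade, and analgesic medication use". It does not say when the form is completed or what period the analgesic item covers.
- Section 4.2 admits Wagner grades 3 and 4. Neither 4.2 nor 4.3 has a criterion on analgesics.
- Section 5.1 places randomisation "immediately after completion of pre-test measurements and prior to the onset of foot care". Section 3 specifies a block list; no stratification factor is named.
- Section 8.2 applies t-tests and chi-square tests "to verify baseline comparability of the intervention and control groups".
- Section 8.4 uses an independent-samples t-test to "compare the magnitude of change (post-test minus pre-test) between the intervention and control groups for each outcome variable". No covariate, stratified analysis or sensitivity analysis appears anywhere in section 8.
- Section 7.4, on the post-test: "The Vital Signs Form, STAI-I, and VAS were re-administered". No record of analgesia is listed there.
- Section 6.2 gives the control arm "routine standard diabetic foot care without any additional intervention". No section says whether analgesia could be given during care, in either arm.

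**The concern.** Pain is a primary outcome, and wound severity and analgesic cover plausibly affect how much it changes over a dressing procedure. The pre-test VAS is taken seated and at rest before care starts, so subtracting it need not remove differences in how painful care of a given wound will be. The investigators collected both variables, and then used them only to ask whether the arms look alike.

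That use has two weaknesses. Outcome variation that the two factors could explain stays in the error term of a trial with only 32 analysed patients per arm. And a non-significant baseline test may be read as evidence that no adjustment is needed, although at this size it lets sizeable imbalances through.

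**Working it through.** **The plan's own figures.** The plan gives no number on covariates. Its only related figure is in section 4.4: 64 patients (32 per group) for d = 0.46, alpha 0.05 and power 0.95. An independent-samples t-test at those values needs 124 per group two-sided, and has 44% power at 32 per group. That mismatch is a separate matter; it is noted here because it explains why the powers below are far from 95%.

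**Inputs.** From the plan: 32 per arm, d = 0.46, two wound grades, alpha 0.05 (taken as two-sided). Assumed, because the documents give no values: 50% prevalence of each binary factor, and the strengths stated at each step.

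**1. Does the section 8.2 test protect the comparison?** Take 19/32 versus 12/32 analgesic users.
- Difference = 7/32 = 0.219; pooled proportion = 31/64 = 0.484.
- SE = sqrt(0.484 × 0.516 × 2/32) = 0.125.
- z = 0.219/0.125 = 1.75, p = 0.08: not flagged.
- With 20 versus 12, z = 0.25/0.125 = 2.0, p = 0.046.

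So the test reacts only at a gap of about 25 percentage points. Under simple randomisation a 50% factor differs between arms by at least 15 points in about 26% of trials, and by at least 20 points in about 10%.

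**2. Is the unadjusted comparison biased?** Over 10,000 simulated trials with no VR effect and two binary factors each shifting the change score by 0.5 or 0.8 residual SD, the unadjusted t-test rejected in 4.8% and 4.7% of trials, with mean estimate about 0. The adjusted analysis rejected in 4.9%. There is no bias and no inflation.

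**3. What precision is lost?** Each factor adds variance 0.25b². With two factors the total is 1 + 0.5b², and the unadjusted SE is sqrt(2(1 + 0.5b²)/32).
- b = 0.5: sqrt(2 × 1.125/32) = 0.265.
- b = 0.8: sqrt(2 × 1.32/32) = 0.287.
- With both factors removed, the SE is at least sqrt(2/32) = 0.250; the simulated values were 0.252 to 0.258.

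For a true effect of 0.46 residual SD:

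| Strength of each factor | Power, unadjusted | Power, adjusted |
|---|---|---|
| 0.5 SD | 40% | 43% |
| 0.8 SD | 36% | 43% |

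These runs adjust a change score for the two factors only. Any further gain from using the pre-test score as a covariate is not counted.

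**4. What if an imbalance has occurred?** Fix the split at 19 versus 12 with no VR effect. The estimate shifts by b × 7/32, which is 0.11, 0.18 or 0.22 SD for b = 0.5, 0.8 or 1.0. The unadjusted test then rejects in about 6.3%, 8.1% or 9.4% of such trials. This is error conditional on the imbalance seen; averaged over all randomisations it returns to the figures in step 2.

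**5. Analgesia after randomisation.** If 10% of one arm and 30% of the other received it, with a 1 SD effect and no VR effect (all assumed), the estimate shifts by 0.20 × 1 = 0.2 SD towards the arm given more, and the type I error is 11% to 12%. Adjusting for the baseline factors does not remove this.

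**The case against.** A reader might infer that the VAS difference could reflect wound severity or analgesic use rather than VR. For factors fixed before allocation, the documents do not support that. Patients are randomised after the pre-test, so these factors differ between arms only by chance, and the t-test's standard error already allows for it. In centimetres, with 50% users and a 1 to 2 cm analgesic effect (assumed), the 95% chance range of the shift is 1.96 × 0.125 × (1 to 2) = 0.25 to 0.49 cm. With an SD of change of 2.0 to 2.5 cm (assumed), the SE is 0.25 × (2.0 to 2.5) = 0.50 to 0.63 cm, so the 95% half-width is about 1.0 to 1.25 cm. The shift is inside that interval and is not an addition to it. Analgesia already acting at the pre-test also partly cancels in the change score. All of this stands.

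It is equally tempting to say that analgesia given during care biased the result. Nothing in the documents says any was given, or that it differed by arm; section 7.3 does not give the form's full content. The most that can be said is that no such record is described. More use in the control arm would dilute a VR benefit, and more in the VR arm would exaggerate one.

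Finally, section 3 has the study ending on June 15, 2025 and section 4.4 reports the completers as analysed. A new form line would recover nothing, and covariates chosen after results are known are not pre-specified. That limits the remedy but does not remove the case for it.

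**Conclusion.** The point holds as one of precision and of misplaced reliance on baseline tests. Wound grade and analgesic use can enter only section 8.2, and the section 8.4 comparison ignores them. The validity of the randomised comparison is not in question on this account: the type I error stays at 4.7% to 4.8% and the mean estimate at about 0. The cost is about 3 to 7 percentage points of power if each factor shifts the outcome by 0.5 to 0.8 residual SD at 50% prevalence; weaker factors would cost less. The failure of the 8.2 test to flag 19 versus 12 needs no assumption beyond 32 per arm.

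The conclusion assumes that the analgesic item describes use before randomisation. Wound grade certainly precedes it, since it is an eligibility criterion. Analgesia between pre-test and post-test is a secondary point inferred from silence, with size and direction unknown.

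**What to change.** - In section 8.4, replace the change-score t-test for VAS and STAI-I with an ANCOVA of the post-test score on arm, pre-test score, wound grade (3 vs 4) and baseline analgesic use (yes/no). Fit it whatever the 8.2 tests show, and label it post hoc if results are already known.
- State in section 7.3 that the analgesic item refers to use before randomisation. If it does not, leave it out of the model.
- In section 8.2, describe the arms and do not use the tests to decide on adjustment.
- Where records exist of analgesia between pre-test and post-test, tabulate it by arm beside the VAS result without adjusting for it, because it follows randomisation. Otherwise state its absence as a limitation of unknown direction.

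The cost is analysis wording and three degrees of freedom: from 64 − 2 = 62 to 64 − 5 = 59. No new patients or measurements are needed.

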### **7.4 Data Collection Procedure**

Data were collected at two time points using a face-to-face interview technique by the principal investigator:

Pre-test: Approximately 5 minutes before the start of foot care (after a minimum 5-minute rest period in the seated position). The Vital Signs Form, STAI-I, and VAS were administered. Participants were then randomized.

Post-test: Immediately after completion of foot care (within 0-2 minutes). The Vital Signs Form, STAI-I, and VAS were re-administered.

To ensure measurement standardization, all measurements were performed by the same researcher using the same equipment with participants in the same position. For blood pressure measurements, patients had rested for  $\geq 5$  minutes in a seated position and had abstained from caffeine for  $\geq 1$  hour and smoking for  $\geq 15$  minutes prior to measurement.

## **8. STATISTICAL ANALYSIS PLAN**

Data analysis was performed using SPSS version 22.0. The level of statistical significance was set at  $\alpha = 0.05$  for all tests.

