## 2. STUDY OBJECTIVES AND HYPOTHESES

### 2.1 Primary Objective

To determine the effect of virtual reality (VR) application during foot care on the pain level, state anxiety, and vital signs (body temperature, oxygen saturation, pulse rate, respiratory rate, systolic and diastolic blood pressure) of individuals with diabetic foot ulcers.

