### 2.2 Study Hypotheses

H1: Virtual reality application during foot care has an effect on pain level in individuals with diabetic foot ulcers.

H12: Virtual reality application during foot care has an effect on state anxiety in individuals with diabetic foot ulcers.

H13: Virtual reality application during foot care has an effect on vital signs in individuals with diabetic foot ulcers.

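### The vital-signs hypothesis is one claim resting on six tests at 0.05 with no decision rule, and the plan places vital signs in the primary objective but lists them as secondary outcomes

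*Combined protocol and SAP*

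**What the plan says.** Section 8 opens with one rule for significance: "The level of statistical significance was set at" 0.05 for all tests. Section 8.4 then compares change scores "between the intervention and control groups for each outcome variable" by independent-samples t-test. Sections 8.1 to 8.5 contain no multiplicity adjustment, testing order or composite.

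Section 7.1 names two primary outcomes, pain (VAS) and state anxiety (STAI-I). Section 7.2 lists six vital signs as secondary outcomes: body temperature, oxygen saturation, pulse rate, respiratory rate, and systolic and diastolic blood pressure. Section 2.1, however, states a single primary objective, the effect of the VR "application during foot care on the pain level, state anxiety, and vital signs", and names all six signs in it.

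Section 2.2 gives three hypotheses of equal standing. Pain and anxiety have one each. The third reads: "Virtual reality application during foot care has an effect on vital signs in individuals with diabetic foot ulcers".

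**The concern.** Pain and anxiety each have one hypothesis and one between-group test. The vital-signs hypothesis has one statement and six tests. The plan does not say whether one, several or all of the six must differ, or whether they are combined. The most permissive choice therefore stays open after the results are seen.

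The placement of vital signs adds to the problem. Because they appear in the primary objective, a single chance finding in, say, oxygen saturation or body temperature could be reported as confirming the third hypothesis and as meeting part of the primary objective. The label in section 7.2 would not permit that second claim. The reader would see p < 0.05 and assume a 5% risk of error for a claim whose real risk could be several times that.

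For the two primaries a smaller question is left open: whether overall success needs both or either one.

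**Working it through.** The plan states no family-wise error rate, so there is no such figure to reproduce. The calculation asks what the stated rules imply.

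**Inputs**
- Per-test level: 0.05 (section 8).
- Sidedness: not stated. The hypotheses are non-directional (for example "Virtual reality application during foot care has an effect on pain level in individuals with diabetic foot ulcers"), so two-sided tests are assumed.
- Number of between-group tests: six for the vital-signs hypothesis (7.2, 8.4) and two for the primaries (7.1, 8.4).
- Correlation between outcomes: not given. A common correlation rho of 0, 0.5 and 0.8 is assumed to show the range.
- All null hypotheses true.
- Decision rule for the third hypothesis: not given. The permissive rule (any one of six) is assumed in order to show what the plan leaves open.

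**Independent tests.** P(at least one p < 0.05) = 1 - (1 - 0.05)^k.
- Six vital signs: 1 - 0.95^6 = 1 - 0.7351 = 0.265.
- Two primaries: 1 - 0.95^2 = 1 - 0.9025 = 0.0975.

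**Correlated tests.** Each test statistic is written as sqrt(rho) × F + sqrt(1 - rho) × E, with F a shared and E a separate standard normal variable, and compared with ±1.96 (500,000 simulated draws).

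| Family | rho = 0 | rho = 0.5 | rho = 0.8 |
|---|---|---|---|
| Six vital signs, any one | 26.5% | 20.7% | 13.9% |
| Two primaries, either one | 9.75% | about 9% | about 8% |

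The 16 within-group paired tests in section 8.3 (eight outcomes × two groups) are not counted.

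**Effect of Holm within each family.** Under no effect, Holm makes at least one false claim only if the smallest p-value passes the first step.
- Six vital signs, first step 0.05/6 = 0.0083: 1 - (1 - 0.0083)^6 = 1 - 0.9510 = 4.9% if independent, and lower with positive correlation.
- Two primaries, first step 0.025: 1 - 0.975^2 = 1 - 0.9506 = 4.9%.
- Both families together, if independent: 1 - 0.9506 × 0.9510 = 9.6%.

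**Cost in power.** Two-sided two-sample t-test, d = 0.46, 32 per group (both from section 4.4):
- at 0.05: 44%;
- at 0.025 (first step for two primaries): 33%;
- at 0.0083 (first step for six vital signs): about 20%.

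The last two figures are lower bounds for each outcome, because later Holm steps are less strict. The d of 0.46 came from work on anxiety and pain, so its use for vital signs is only illustrative. The 44% also disagrees with the power of 0.95 stated in section 4.4. That is a separate sample-size matter and is not needed for this point.

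**The case against.** **The rule that any one of six suffices is an inference.** This stands. Section 2.2 gives no rule at all. The defect is that the rule is unspecified, and the 21-26% figures (rho 0.5 to 0) describe what the plan permits, not what it says will be done.

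**A reader might pool all eight outcomes.** Doing so gives 1 - 0.95^8 = 33.7% if independent, or about 25% at rho = 0.5, as the risk of falsely claiming that VR works. The documents do not support that as the headline. They state three separate hypotheses and never make an omnibus claim across all eight outcomes.

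**Pain and anxiety may need no joint control.** Each has its own hypothesis and one between-group test, so each keeps a 5% error rate for its own claim. Whether separately stated hypotheses need joint control is debated. It would be wrong to infer that the primaries necessarily run at about 10%: that holds only if success on either one is presented as overall success, which the plan does not say.

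**Vital signs are only secondary.** Section 7.2 says so, and many trials leave secondary outcomes unadjusted. This answer fails here because section 2.1 places the same signs in the primary objective, section 2.2 gives them a formal hypothesis, and nothing marks them as exploratory.

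**The range depends on correlations the documents do not give.** True, and the risk falls as correlation rises. At rho = 0.8 it is still 13.9%, more than twice 5%.

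**Conclusion.** The concern holds for the third hypothesis. As written, it has no decision rule. Under the most permissive reading that the text leaves open, its false-positive risk is 26.5% with independent outcomes, 20.7% at rho = 0.5 and about 14% at rho = 0.8. These figures assume two-sided tests, no true effect on any vital sign, and equal correlation among the six. The conflict between section 2.1 and section 7.2 over the status of vital signs is a plain inconsistency and depends on no assumption.

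For the two primaries the point is narrower: a joint risk of about 9-10% (rho 0.5 to 0) if either one counts as overall success, and no inflation of each separate claim otherwise.

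This should be corrected, but it does not by itself undermine the separate analyses of pain and state anxiety.

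**What to change.** 1. Make section 2.1 match sections 7.1 and 7.2: pain and state anxiety primary, vital signs secondary.
2. In section 8, apply Holm across the six vital-sign between-group tests, and count the third hypothesis as supported only by a Holm-adjusted p < 0.05. Otherwise report vital signs as exploratory and make no claim from them.
3. State whether overall success needs both primary outcomes or either one. If either one suffices, apply Holm across the two.
4. The study period in section 3 ended in June 2025 and sections 4.4 and 8 describe the analyses as done. Report adjusted p-values beside the unadjusted ones, and disclose the adjustment and any rewording of the objective as post hoc.

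No new data are needed, since Holm can be applied to the existing p-values. The scheme controls error at 0.05 within each family, not across both. With Holm on both families, about 9.6% remains across all eight outcomes if independent, which suits a split into primary and secondary outcomes but should be stated. The price is the lower per-outcome power shown in the working.
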